5.1.1. Inclusion criteria

Patients who meet all of the following criteria can be enrolled:

- 1. Patients over the age of 18 years
- 2. Patients treated with a targeted therapy (sunitinib, everolimus), or by other treatments (interferon, or radionuclide therapy, or chemotherapy or a somatostatin analogue)* for:

*patients who are started on a 1^{st} , 2^{nd} , 3^{rd} or 4^{th} line of treatment (targeted therapy or other treatment) at the time they are enrolled (incident cases) or patients whose 1^{st} , 2^{nd} , 3^{rd} or 4^{th} line of treatment is ongoing as long as this treatment was started at the site that is enrolling the patient in the study (prevalent cases); a change of treatment line is defined as a change of drug or combination thereof.

- a neuroendocrine tumour of the pancreas, that is unresectable or metastatic and confirmed by histology,
- well-differentiated,
- with disease progression prior to initiation of treatment in the investigator's opinion (clinical or radiological progression),
- 3. Patients who have been informed about the study design and have signed the informed consent form.

Patients who are participating in another observational study can still be enrolled. Moreover, it will be important to enrol patients from clinical trials since the follow-up bias this could entail (connected to the schedule and terms of follow-up imposed by the trial) will have less impact than selection bias, which could lead to this study only including patients who are not eligible for clinical trials. However, in order to identify and categorise patients into the different groups of interest, patients participating in a clinical trial will be able to be included if they are in a treatment arm in the trial with a treatment that has been validated with an MA (Marketing Authorisation) and by the TNCD

final version of 17/07/2018

(Thésaurus National de Cancérologie Digestive; French thesaurus of gastrointestinal oncology) based on the versions of December 2013, if the clinical trial is not double blinded and if patients are not included in the placebo arm in a placebo-controlled trial.

5.1.2. Exclusion criteria:

The following patients may not be included in the study:

- 1. Patients with a diagnosis of poorly differentiated neuroendocrine carcinoma or adenoneuroendocrine carcinoma.
- 2. Patients receiving a targeted therapy (everolimus or sunitinib) that they have already received in an earlier treatment line (patient in rechallenge).

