5.9.3. Therapeutic Pathway of Patient

The therapeutic pathway of the patient will be described based on the three treatments (main treatment line: Targeted therapy, Chemotherapy and Somatostatin analogs).

Targeted therapy

The targeted therapy will be described for each period (overall follow-up, before inclusion, after inclusion) and as follows:

- Number of patients having received at least one targeted therapy.
- Number of patients having received Everolimus at least once.
- Number of patients having received Sunitinib at least once.
- Number of patients having received Pazopanib at least once.
- Number of patients having received Everolimus at least once and Sunitinib at least once.
- Number of patients having received Everolimus at least once, but not Sunitinib or Pazopanib.
- Number of patients having received Sunitinib at least once, but not Everolimus or Pazopanib.
- Number of patients who never received targeted therapy.
- Number of targeted therapies received per patient (quantitative and by class: 0 / 1 / 2 / 3 / 4 and more).

Targeted therapy will be described for the entire follow-up based on:

• Number of patients having received two different targeted therapies (Everolimus and Sunitinib, or Everolimus and Pazopanib).

In addition, the position of the targeted therapy in the care pathway of the patient will be described for the entire follow-up:

- Number of patients having received a targeted therapy as the 1st, 2nd, 3rd, nth main treatment line.
- Number of patients having received a targeted therapy immediately before/after chemotherapy.
- Number of patients having received a targeted therapy immediately before/after a somatostatin analog (as main treatment).

The duration of the targeted therapy (in months) and reasons for the discontinuation will also be described irrespective of the targeted therapy and by differentiating between Everolimus and Sunitinib during the period before inclusion then after inclusion.

The total duration of the targeted therapy (obtained by adding the periods before inclusion and after inclusion) will be described.

The analysis and duration of the targeted therapy (irrespective of the targeted therapy) and the reasons for the discontinuation will also be presented based on the following subgroups:

- Main treatment lines during follow-up (1/2/.../n).
- Number of patients with ≤ 2 lines, ≥ 2 main treatment lines for the entire follow-up.
- Ki67 (the most recent prior to inclusion) ($\leq 10\% / > 10\%$).

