- Liver invasion at initiation of the ongoing treatment line or line started at inclusion $(\le 50\% / > 50\%)$.
- Number of metastatic sites when starting the current line of treatment or line of treatment started at inclusion (≤2 / >2). The "not reported" modality will be considered as missing data.

Chemotherapy

Chemotherapy will be described for each period (overall follow-up, before inclusion, after inclusion) and as follows:

- Number of patients having received chemotherapy at least once.
- Number of patients having never received chemotherapy.
- Number of chemotherapies received per patient (quantitative and by class: 0 / 1 / 2 / 3 / 4 and more).

• Number of patients having received chemotherapy and a somatostatin analog as main treatment.

In addition, the position of chemotherapy in the care pathway of the patient will be described for the entire follow-up:

- Number of patients having received chemotherapy as the 1st, 2nd, 3rd, nth main treatment line.
- Number of patients having received chemotherapy immediately before/after targeted therapy.
- Number of patients having received chemotherapy immediately before/after a somatostatin analog (as main treatment).
- Number of patients having received chemotherapy as 1st line at inclusion then targeted therapy as 2nd line (yes/no).
- Number of patients having received alkylating chemotherapy after inclusion (yes/no).
- Number of alkylating chemotherapies received after inclusion.

Alkylating agents are listed in Appendix 10.2.

Somatostatin analogs

Somatostatin analogs will be described for each period (entire follow-up, prior to inclusion, after inclusion) overall (main or combination treatment), if received as a main or combination treatment and as follows:

- Number of patients having received at least one somatostatin analog.
- Number of patients having never received a somatostatin analog.
- Number of somatostatin analogs received per patient (quantitative and by class: 0 / 1 / 2 / 3 / 4 and more).

In addition, the position of the somatostatin analog in the care pathway of patients will be described for the entire follow-up:

- Number of patients having received a somatostatin analog as the 1st, 2nd, 3rd, nth main treatment line.
- Number of patients having received a somatostatin analog in combination as the 1st, 2nd, 3rd, nth main treatment line.
- Number of patients having received a somatostatin analog as the 1st, 2nd, 3rd, nth main treatment line or in combination.

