Number of patients having received a targeted therapy immediately after chemotherapy	XX (XX.X%)
Number of patients having received a targeted therapy immediately before a somatostatin analoganalog (as main treatment)	XX (XX.X%)
Number of patients having received a targeted therapy immediately after a somatostatin analoganalog (as main treatment)	XX (XX.X%)

Programmer note: add as a footnote the list of patients whose start date for their last main treatment line falls after the date of the last visit.

Table 14.2.2.2.1.5: Length and Reason for Discontinuation of Targeted Therapy

- Reference Set - Analysis of the Period before Inclusion

		Total
		(N=XX)
Length of targeted therapy before inclusion (months) (1)	N	XX
	Missing data	XX
	Mean (SD)	XX.XX (X.XX)
	Mean	XX.X
	[Min; Max]	[XX.X; XX.X]
	[Q1; Q3]	[XX.X; XX.X]
Length of Everolimus targeted therapy before inclusion (months) (1)	N	XX
	Missing data	XX
	Mean (SD)	XX.XX (X.XX)
	Mean	XX.X
	[Min; Max]	[XX.X; XX.X]
	[Q1; Q3]	[XX.X; XX.X]
Length of Sunitinib targeted therapy before	N	XX
inclusion (months) (1)	Missing data	XX
	Mean (SD)	
	Mean	XX.XX (X.XX)
		XX.X
	[Min; Max]	[XX.X; XX.X]
	[Q1; Q3]	[XX.X; XX.X]
Reason for discontinuation of targeted therapy before inclusion (2)	N	XX
	Missing data	XX
	Adverse event*	XX (XX.X%)
	Progression	XX (XX.X%)
	Planned discontinuation of	XX (XX.X%)
	treatment	727 (777.7770)
	Patient decision	VV (VV V0/.)
		XX (XX.X%)
	Other	XX (XX.X%)
Reason for discontinuation of Everolimus targeted therapy before inclusion (2)	N	XX
	Missing data	XX
	Adverse event*	XX (XX.X%)
	Progression	XX (XX.X%)
	Planned discontinuation of	XX (XX.X%)
	treatment	
	Patient decision	XX (XX.X%)
	Other	XX (XX.X%)
Reason for discontinuation of Sunitinib targeted therapy before inclusion (2)	N	XX
2 17 (-/	Missing data	XX
	Adverse event*	XX (XX.X%)
	Progression	XX (XX.X%)
	Planned discontinuation of	
	treatment	XX (XX.X%)
	Patient decision	XX (XX.X%)
	Other	XX (XX.X%)
		()

^{*} The "Total" column shows all of the targeted therapies.

⁽¹⁾ Data reported directly from the e-CRF, total of data if several targeted therapies.

⁽²⁾ The number of reasons for discontinuation will be higher than the set having received targeted therapy (ie, patients having discontinued Everolimus and Sunitinib).

⁽³⁾ Total duration representing the entire follow-up period (before and after inclusion).

Using the same template:

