Table 14.2.2.2.1.6: Length and Reason for Discontinuation of Targeted Therapy in the Care Pathway of Patients – Reference Set – Analysis of the Period before and after Inclusion

Table 14.2.2.2.1.7: Length and Reason for Discontinuation of Targeted Therapy in the Care Pathway of Patients – Reference Set – Analysis of the Entire Follow-Up Period

Table 14.2.2.2.1.8: Length and Reason for Discontinuation of Targeted Therapy

- Reference Set - Subgroup Analysis Based on the Number of Main Treatment

Line Throughout Follow-Up

		1 st Line (N=XX)	2 nd Line (N=XX)	 (N=XX)	N th Line (N=XX)
Length of targeted therapy (months)	N	XX	XX	XX	XX
)	Missing data	XX	XX	XX	XX
	Mean (SD) Mean	XX.XX (X.XX) XX.X	XX.XX (X.XX) XX.X	XX.XX (X.XX) XX.X	XX.XX (X.XX) XX.X
	[Min; Max] [Q1; Q3]	[XX.X; XX.X] [XX.X; XX.X]	[XX.X; XX.X] [XX.X; XX.X]	[XX.X; XX.X] [XX.X; XX.X]	[XX.X; XX.X] [XX.X; XX.X]
Reason for discontinuation of targeted therapy	N	XX	XX	XX	XX XX
0 17	Missing data	XX	XX	XX	
	Adverse event*	XX (XX.X%)	XX (XX.X%)	XX (XX.X%)	XX (XX.X%)
	Progression	XX (XX.X%)	XX (XX.X%)	XX (XX.X%)	XX (XX.X%)
	Planned discontinuation of treatment	XX (XX.X%)	XX (XX.X%)	XX (XX.X%)	XX (XX.X%)
	Patient decision	XX (XX.X%)	XX (XX.X%)	XX (XX.X%)	XX (XX.X%)
	Other	XX (XX.X%)	XX (XX.X%)	XX (XX.X%)	XX (XX.X%)

Using the same template:

Table 14.2.2.2.1.9: Length and Reason for Discontinuation of Targeted Therapy Over the Entire Follow-Up Period – Reference Set – Subgroup Analysis Based on the Number of Main Treatment Lines Throughout Follow-Up (≤2 Lines, >2 Lines)

Table 14.2.2.2.1.10: Length and Reason for Discontinuation of Targeted Therapy Over the Entire Follow-Up Period − Reference Set − Subgroup Analysis Based on the Ki67 (≤10%, >10%)

Table 14.2.2.2.1.11: Length and Reason for Discontinuation of Targeted Therapy Over the Entire Follow-Up Period – Reference Set – Subgroup Analysis Based on the Percentage of Liver Invasion (≤50%, >50%)

Table 14.2.2.2.1.12: Length and Reason for Discontinuation of Targeted Therapy Over the Entire Follow-Up Period – Reference Set – Subgroup Analysis Based on the Number of Metastatic Sites at Initiation of the Current Treatment Line or Treatment Line Started at Inclusion (≤2 Sites, >2 Sites)

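### Targeted-therapy duration and stop reason before plus after inclusion are split by liver invasion and site count read only at the inclusion line, so for earlier courses the grouping follows the outcome; for Ki67 the order is unknown

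*SAP*

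**What the plan says.** SAP 5.9.3 (Targeted therapy) defines the outcome: "The total duration of the targeted therapy (obtained by adding the periods before inclusion and after inclusion) will be described". The next sentence introduces the split: "The analysis and duration of the targeted therapy (irrespective of the targeted therapy) and the reasons for the discontinuation will also be presented" by a list of subgroups. Three of these are disease markers:

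- "Ki67 (the most recent prior to inclusion"), cut at 10%;
- "Liver invasion at initiation of the ongoing treatment line or line started at inclusion", cut at 50%;
- number of metastatic sites, taken at the same moment as liver invasion and cut at 2.

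The corresponding Tables 14.2.2.2.1.10 to 14.2.2.2.1.12 are titled "Length and Reason for Discontinuation of Targeted Therapy Over the Entire Follow-Up Period". Footnotes to the template in SAP 9.3.2.1.1 explain the scope: "Total duration representing the entire follow-up period (before and after inclusion"), and for pre-inclusion lengths "Data reported directly from the e-CRF, total of data if several targeted therapies".

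Patients may enter with an earlier targeted therapy. Protocol 5.1.2 bars only a targeted therapy "that they have already received in an earlier treatment line (patient in rechallenge"). SAP 5.9.1 and 5.9.7 plan subgroups for patients with one, or at least two, targeted therapies before inclusion.

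**The concern.** A table of treatment duration by liver burden, number of sites or Ki67 will be read as showing how long targeted therapy lasts, and why it stops, in patients who had that level of disease when they began it. That reading needs the marker to come before the course. For a targeted therapy given and ended before the inclusion line, liver invasion and site count come after it.

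Two distortions follow. A longer earlier course leaves more time for burden to grow, so long duration can look linked to worse disease. An earlier course that stopped for progression may itself have raised the burden or added the site that later sets the patient's group, so the split of stop reasons is partly circular. At stake is a misleading clinical reading of three descriptive tables by prognostic marker.

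**Working it through.** The plan states no figure for this point. The check is first one of time order, then of possible size.

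**Time order, by when the targeted therapy was given**

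| Targeted therapy | Liver invasion and sites | Ki67 |
|---|---|---|
| Ended before the inclusion line | read after the course | unknown |
| The inclusion line itself | read at its start | unknown in prevalent patients, since the latest value before inclusion may postdate the start of the line |
| Started after inclusion | read before the course | read before the course |

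No better marker exists for the first row. The CRF table of previous treatments (CRF 2.4) records drug, line, somatostatin-analogue combination, duration (targeted therapies only) and stop reason. It holds no Ki67, liver invasion or site count at the start of those lines. The CRF asks for a Ki67 value without a date, and Table 14.1.4.1.9 gives time since Octreoscan and PET but not since Ki67. By eligibility, the inclusion line also starts after progression.

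The SAP draws the right boundary elsewhere. By-line PFS (5.9.7) and OS (5.9.8) use only the inclusion line and later lines, because information on earlier lines is judged insufficient. The three tables here carry no such limit.

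**Possible size: burden rising with time.** All inputs are assumptions. Every patient has targeted therapy in the inclusion line; 10, 30 or 50% also had an earlier one; each course is exponential with mean 10 months; burden rises 0, 0.03 or 0.06 SD per month of earlier therapy; the high group is the top 30% at the inclusion line; 400,000 simulated patients per setting. With no true marker effect, the high-minus-low gap in mean total duration is:

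| Earlier targeted therapy | Growth 0 | 0.03 SD/month | 0.06 SD/month |
|---|---|---|---|
| 10% | about 0 | +1.0 | +1.7 |
| 30% | about 0 | 14.87 − 12.21 = +2.7 | 16.38 − 11.60 = +4.8 |
| 50% | about 0 | 17.71 − 13.84 = +3.9 | 19.81 − 12.91 = +6.9 |

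As a check, in the 30%, 0.06 cell the overall mean should be 10 + 0.3 × 10 = 13.0 months, and 0.3 × 16.38 + 0.7 × 11.60 = 13.0.

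Now suppose a true adverse effect (−0.2 on log mean duration per SD), with burden growing. Splitting by the marker at the first targeted therapy gives about −3.5 to −4.6 months. The planned split gives −2.5 to −1.5 (10% with earlier therapy), −1.3 to +1.2 (30%) and −0.6 to +3.1 (50%), so the association is attenuated and can change sign. Restricted to the inclusion line, the gap is within 0.1 month of 0 under no effect and about −3.1 to −3.3 under the true effect.

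**Possible size: fixed growth per course.** Growth need not depend on duration for a gap to appear, because duration is summed per patient. Assume a mean of 12 months per course, liver burden at first therapy uniform on 5 to 60%, and growth of g points over an earlier course whatever its length. A share p of patients had an earlier course. The chance of exceeding 50% is 10/55 without an earlier course and (10 + g)/55 with one.

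- p = 0.2, g = 6: share with an earlier course is 0.2 × 16 / (0.2 × 16 + 0.8 × 10) = 0.286 above 50%, and 0.2 × 39 / (0.2 × 39 + 0.8 × 45) = 0.178 at or below. Gap = 12 × (0.286 − 0.178) = 1.3 months.
- p = 0.4, g = 12: 0.4 × 22 / (0.4 × 22 + 0.6 × 10) = 0.595, and 0.4 × 33 / (0.4 × 33 + 0.6 × 45) = 0.328. Gap = 12 × (0.595 − 0.328) = 3.2 months.

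Patients with an earlier course have both a longer total and a higher recorded burden.

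**The case against.** The strongest objection is about size. SAP 5.5.1 notes that treatment is changed in practice after progression. If a course ends at progression, growth over the course is tied to that event and not to its length, and slow growers stay on treatment longest. In a model with one course per patient and fixed growth per course, the spurious gap is indeed 0. This stands as a warning against quoting a single magnitude. It does not remove the problem, because the planned parameter is a per-patient sum, and under that sum fixed growth still gives a gap.

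Three further points stand. Ki67 may come from a biopsy taken before the earlier therapy, so reversed order is not shown for it. The number of patients with earlier targeted therapy is unknown; the exclusion in the protocol summary, read literally, would leave few, although Protocol 5.1.2, the CRF and the SAP all provide for them. And the tables are descriptive, with no test planned; the title of Table 14.2.2.2.1.12 states openly when the site count is taken.

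A reader might infer that the planned split cannot be computed for earlier courses. It can: duration by marker status at the inclusion line is fully derivable from the CRF. What is unavailable is the marker at the start of each earlier course. A reader might also infer that the tables will show longer duration with worse disease. The documents support only that they could; if worse disease truly shortens treatment, the split may merely dilute that.

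**Conclusion.** The time-order defect is established from the documents for liver invasion and number of metastatic sites, and only for targeted therapy that ended before the inclusion line. Courses in the inclusion line have a proper baseline for these two markers, and courses started after inclusion have all three markers beforehand. For Ki67 the order cannot be established either way.

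The size is not determined by the documents. With no true effect it is 0 if there is no earlier targeted therapy or no growth in burden, and several months under the assumptions worked above; none of those inputs comes from the protocol or SAP. Only duration by a burden marker was modelled; for stop reasons the argument is one of time order alone. Primary PFS, OS and safety are unaffected. The point is worth correcting because the remedy is cheap and the tables invite a prognostic reading.

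**What to change.** In SAP 5.9.3 and in Tables 14.2.2.2.1.10 to 14.2.2.2.1.12, restrict the three marker splits to targeted therapy in the inclusion line or started later, and label liver invasion and site count as read at the start of the inclusion line. Limiting the tables to the inclusion line alone would needlessly drop later courses, for which the markers do precede the outcome. Alternatively, keep all courses but show pre-inclusion ones in a separate column with a footnote on marker timing.

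Keep pre-inclusion durations in the unstratified Tables 14.2.2.2.1.5 and 14.2.2.2.1.7. Label Ki67 as most recent before inclusion, date not collected.

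The cost is one sentence in the SAP, three table titles and a footnote; no new data are needed. The downside is fewer targeted-therapy courses in three descriptive tables.

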5.9.4. Sequence of Treatment Lines

The main treatment lines (targeted therapy, chemotherapy, somatostatin analog, etc.) will be presented by sequence for the entire follow-up, before inclusion, at inclusion and after inclusion. For each sequence, the number of patients in each sequence will be presented. This analysis will be duplicated by providing details of the targeted therapies (Everolimus, Sunitinib and Pazopanib). The main concomitant treatment lines will also be presented with a detailed description of the targeted therapies.

5.9.5. Discontinuation Due to Toxicity

Discontinuation due to toxicity (AE or death) of the main treatment line will be described for the period after inclusion. The number of patients with at least one discontinuation due to toxicity and the number of discontinuations due to toxicity will be described based on:

- The main treatment ongoing at inclusion (Targeted therapy (of any kind, then Everolimus and Sunitinib), Chemotherapy, Somatostatin analog).
- Number of lines for the entire follow-up (≤ 2 lines, ≥ 2 lines).
- Number of targeted therapies received for the entire follow-up (0, 1, 2, >2).
- Targeted therapy received as 2nd line main treatment vs Chemotherapy received as 2nd line main treatment for the entire the follow-up period.

